6.3 Subgroup and Sensitivity Analyses

Exploratory subgroup analyses of the primary efficacy endpoint by baseline characteristics, e.g. age group and gender, will be performed using the analysis method described in Section 6.1, if appropriate.

If an ITT subject did not have an onset of COVID-19 signs and symptoms within 7 days prior to Screening, a sensitivity analysis of the primary efficacy endpoint will be carried out using the analysis method described in Section 6.1.

Additional analyses may be performed to gain a better understanding but would not replace analyses planned for primary and secondary efficacy endpoints.

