4. GENERAL CONSIDERATIONS FOR DATA ANALYSIS

Unless otherwise specified, continuous variables will be summarized using descriptive statistics

(n, mean, standard deviation, median, minimum, and maximum). Categorical variables will be summarized showing the number and percentage of subjects within each category.

Summary results will be provided for each treatment group. All tabulations will be based on pooled data across centers.

Unscheduled visits will be excluded from the summaries but will be included in the data listings.

All statistical tests will be two-sided and tested at the 5% level of significance.

Analyses will be performed using SAS for Windows statistical software, version 9.4 or higher (SAS, Cary, NC), except where other software may be deemed more appropriate.

CTI will perform all efficacy and safety analyses described in this SAP.

Subject data will be listed, sorted by treatment group and subject number. When applicable, listings will be additionally sorted by visit and assessment date/time.

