4.5 Multiple Comparisons

Because of the exploratory nature of this study, there will be no adjustment for multiple comparisons.

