6.1 Primary Efficacy Endpoint and Analysis

The primary efficacy variable is the clinically meaningful worsening of COVID-19 within 28 days from the start of experimental therapy.

The Ordinal Scale for Clinical Improvement is a 9-point scale that measures disease severity. For this study, an increase of 2 or more points is considered meaningful worsening of disease ([Table 2](#)). This endpoint considers changes in disease severity that are observed at any time over the course of this study.

The Ordinal Scale for Clinical Improvement to be used in this study is derived from a draft scale proposed by the World Health Organization^[1] for clinical improvement as presented below:

Table 2 Ordinal Scale for Clinical Improvement (Derived from draft WHO scale)^[1]

Descriptor	Score
No clinical or virological evidence of infection	0
Infected but no limitation of activities	1
Limitation of activities	2
Hospitalized not requiring oxygen therapy (SpO ₂ > 93% on room air)	3
Oxygen by mask or nasal prongs	4
Non-invasive ventilation or high-flow oxygen	5
Intubation and mechanical ventilation	6
Ventilation + additional organ support- pressors, RRT, ECMO	7
Death	8

The null hypothesis is that there is no difference in proportions of subjects with clinically meaningful worsening of COVID-19 through Day 29 between randomized treatment groups; $H_0: \pi_t - \pi_c = 0$. The alternative hypothesis is that the proportions of subjects with clinically meaningful worsening of COVID-19 through Day 29 are different between the treatment groups; $H_1: \pi_t - \pi_c \neq 0$.

Subjects who had an increase of 2 or more points in Ordinal Scale from the baseline will be treated as meeting the criteria for clinically meaningful worsening of COVID-19. The proportion of subjects who met the criteria within each treatment group will be presented along with a two-sided exact (Clopper-Pearson) 95% confidence interval (CI).

The observed difference in the proportion of subjects meeting the criteria between treatment groups along with the exact unconditional 95% CI for risk difference will be calculated. The null hypothesis will be tested using Fisher's exact method and the p-value will be reported.

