9. SAMPLE SIZE AND POWER CALCULATIONS

The trial size of 100 subjects (50 PUL-042 inhalation solution: 50 placebo) was chosen based on clinical considerations. The rates of infection to adequately estimate a sample size for a statistically significant result are unknown.

Enrolled subjects will be randomized with equal probability to receive blinded treatment consisting of either PUL-042 or placebo.

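### The planned subgroup analyses test for an effect within each age group and gender but give no estimate or test of whether the effect differs between levels.

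*SAP*

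**What the plan says.** On subgroups, SAP 6.3 says: "Exploratory subgroup analyses of the primary efficacy endpoint by baseline characteristics, e.g. age group and gender, will be performed using the analysis method described in" the primary-endpoint section (SAP 6.1). The sentence closes with a qualifier that makes these analyses conditional on being appropriate.

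Section 6.1 of the SAP has three parts: a Clopper-Pearson interval for the proportion in each arm; the difference in proportions, "along with the exact unconditional 95% CI for risk difference will be calculated"; and a test: "The null hypothesis will be tested using Fisher's exact method and the p-value will be reported". The null hypothesis is no difference between the randomized arms.

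Two general rules also apply. SAP 4 says: "All statistical tests will be two-sided and tested at the 5% level of significance". SAP 4.5 says: "Because of the exploratory nature of this study, there will be no adjustment for multiple comparisons".

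The SAP does not define the age groups or list the full set of subgroup factors. Neither the protocol nor the SAP mentions an interaction or heterogeneity analysis.

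**The concern.** Carried into a subgroup, the Section 6.1 test asks whether PUL-042 differs from placebo in that subgroup. A breakdown by age or gender is normally read for something else: whether the effect is larger in one level than in the other. A p-value below 0.05 in one level beside a p-value above 0.05 in the other does not answer that. With about 25 subjects per arm in a level, such a pattern can arise from low power alone.

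The Background section of the protocol says the data will inform the feasibility of Phase 3. If the overall result were positive, a table with one significant and one non-significant level could be taken as a sign that the drug works in only part of the population, and nothing in the planned output measures the difference directly.

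**Working it through.** The documents state no event rate, effect size or power for the primary endpoint or for subgroups, so there is no figure of the plan's own to reproduce. The event rates below are assumptions, shown as a range.

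**Inputs**
- 50 per arm, equal allocation: "The trial size of 100 subjects (50 PUL-042 inhalation solution: 50 placebo) was chosen based on clinical considerations" (SAP 9).
- Two-sided 5% Fisher test (SAP 4 and 6.1).
- Assumed: a factor with two equal levels, so 50 / 2 = 25 per arm per level.
- Assumed: the same placebo rate and the same PUL-042 rate in both levels (a uniform effect).

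**Step 1. Power within one level.** All 26 x 26 possible tables were enumerated. s is the total binomial probability of those with Fisher p ≤ 0.05.

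**Step 2. Pattern across the two levels.** The levels are independent, so P(exactly one significant) = 2s(1 − s), P(both) = s², and P(neither) = (1 − s)². For 20% v 5%, s = 0.198, and 2 x 0.198 x 0.802 = 0.318.

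| Placebo v PUL-042 | Whole-trial power | s | Exactly one | Both | Neither |
|---|---|---|---|---|---|
| 10% v 5% | 6.3% | 0.013 | 2.6% | 0.0% | 97.4% |
| 15% v 5% | 24.4% | 0.072 | 13.4% | 0.5% | 86.1% |
| 20% v 10% | 19.5% | 0.086 | 15.7% | 0.7% | 83.6% |
| 30% v 15% | 35.4% | 0.150 | 25.5% | 2.2% | 72.3% |
| 20% v 5% | 50.8% | 0.198 | 31.8% | 3.9% | 64.3% |
| 40% v 20% | 51.5% | 0.231 | 35.5% | 5.3% | 59.2% |
| 30% v 10% | 64.0% | 0.305 | 42.4% | 9.3% | 48.3% |
| 40% v 15% | 75.8% | 0.383 | 47.3% | 14.7% | 38.0% |

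**Step 3. Trials with a significant overall result** (simulation, 200,000 trials per case, placebo rates 15-50%). Exactly one level is significant in 52-58% of these trials when the effect gives 80% overall power, and in 39-63% when it gives 50%.

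**Step 4. What a direct comparison of levels would show.** With x PUL-042 events and y placebo events out of 25 in level k, the log odds ratio is L_k = log[(x + 0.5)/(25.5 − x)] − log[(y + 0.5)/(25.5 − y)]. Its variance is V_k = 1/(x + 0.5) + 1/(25.5 − x) + 1/(y + 0.5) + 1/(25.5 − y). The interaction statistic is (L_1 − L_2)/√(V_1 + V_2), compared with ±1.96. In the Step 3 uniform-effect cases, extended to 90% overall power, it rejects in 0.0-4.7% of trials.

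**Step 5. Choice of scale.** A Wald test on the difference between the two risk differences rejects in 4.4-5.6% of trials for the four larger-effect rows (20% v 5%, 40% v 20%, 30% v 10%, 40% v 15%), where placebo risk is the same in both levels. That assumption is doubtful for age. Suppose instead that the relative risk is constant but placebo risk differs between levels: 15% v 5% and 45% v 15%; 10% v 5% and 60% v 30%; 10% v 3.3% and 50% v 16.7%. The risk-difference test then rejects in 28-46% of trials and the log-odds-ratio test in about 4-5%.

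**Step 6. Power of the interaction test.** If one level has the full effect (20% v 5%, 30% v 10% or 40% v 15%) and the other has none, power is only about 13-29%.

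**The case against.** The strongest defence is that the plan promises little. The subgroup analyses are labelled exploratory, are to be done only if appropriate, and belong to a study that openly waives multiplicity control. The SAP states no rule for reading subgroup p-values and claims no conclusion about heterogeneity. All of this stands and keeps the point minor. It does not make the within-level test answer the question of whether effects differ.

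A reader might infer that p-values are the only inferential subgroup output. They are not. Section 6.1 applied by level also gives a risk difference with an exact 95% CI, so two levels can be compared by eye. What is missing is the contrast between them.

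A reader might also infer that a uniform effect will often look subgroup-specific whatever the event rate, or that the discordance rate can be expressed as a multiple of 5%. The documents support neither. They give no rate for this endpoint, and in the lower rows of the table neither level is significant in 84-97% of trials. A pattern of two p-values is also not a test with a nominal level. Likewise, no passage links subgroup results to the choice of a Phase 3 population, so a wrongly restricted population is a possibility and not a planned consequence.

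Finally, an interaction test has low power here and depends on its scale. Both are true and shape the fix. They argue for leading with an estimate and its interval, and against treating a risk-difference interaction as the only evidence.

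**Conclusion.** The point holds as a minor, inexpensive improvement. SAP 6.3 repeats an unadjusted 5% Fisher test within each subgroup level and plans no estimate or test of whether the effect differs between levels.

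Its size is conditional. With two equal levels, 25 per arm in each and a uniform effect, exactly one level is significant in about 32-47% of trials for effects from 20% v 5% to 40% v 15%, where the whole trial has roughly 51-76% power. For 10% v 5% to 20% v 10% the figure is about 3-16%. The even split and all the rates are assumptions. With an uneven split of 15 and 35 per arm, the pattern ranges from 3.6% (10% v 5%) to 61% (30% v 5%).

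The concern therefore matters mainly if the trial shows an overall effect, which is also when subgroup tables are most likely to be read closely. The primary analysis is not affected.

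**What to change.** In SAP 6.3, replace the subgroup sentence with wording such as:

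> For each subgroup level, the number of subjects, the number of events and the risk difference with 95% CI will be presented without a p-value. For each factor, the treatment-by-subgroup interaction will be estimated as a ratio of odds ratios with 95% CI and p-value, using a small-sample method (exact or Firth logistic regression, or a 0.5 correction). Subgroup differences are exploratory and will be judged from the interaction estimate, not by comparing significance within levels. A non-significant interaction will not be taken to show a uniform effect.

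Name one of the three small-sample methods before unblinding. Leave the symptom-onset sensitivity analysis in the same section unchanged.

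The cost is a few lines of SAP text and one contrast per factor, with no new data or subjects. The downside is a wide interaction interval and low power with 100 subjects. The odds-ratio scale is also a choice: an effect that is constant as a risk difference would not be constant on it, so the per-level risk differences should stay in the table beside the interaction estimate.

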7. SAFETY AND TOLERABILITY ANALYSIS

Safety and tolerability assessments will include adverse events (AEs), vital signs, and pulmonary function tests. If there is a difference between the ITT set and SAF set, then all safety summaries (or analyses if applicable) will be conducted using the SAF set. Otherwise, the ITT set will be used. No formal hypothesis testing will be performed to compare differences between treatment groups.

7.1 Extent of Exposure and Compliance

The number of doses received will be summarized by treatment group. The duration of study drug administration in minutes, the reason for study drug discontinuation, and whether 100% of study drug (4 mL) was delivered will be summarized for each dose by treatment group.

7.2 Adverse Events

The AE reporting period for this study is continuous and begins at the time of randomization to study treatment and ends on Day 29. All AEs (both serious and nonserious) must be followed until resolution or until a stable clinical endpoint is reached. All measures required for AE management and the ultimate outcome of the AE must be recorded in the source documentation and in the eCRF.

AEs will be classified by SOC and PT using the most recent version of MedDRA.

7.2.1 Treatment-emergent Adverse Events

Treatment-emergent AEs are defined as those that begin or worsen after the start of study drug administration.

For adverse events with incomplete start dates, the same imputation algorithm for partial date information as described in Section 5.6 will be used for the determination of an AE being treatment emergent or not. Briefly, the unknown portions of an AE onset date will be imputed to the latest possible before being compared to the date of first study drug administration.

7.2.2 Adverse Event Severity

The severity (i.e., grade) of an AE will be assessed by the Investigator according to the definitions in the Common Terminology Criteria for Adverse Events (CTCAE) v5.0. If the AE is not specifically listed in the reference above, the following grades should be used:

- Grade 1 Mild; asymptomatic or mild symptoms; clinical or diagnostic observations only; intervention not indicated
- Grade 2 Moderate; minimal, local or noninvasive intervention indicated; limiting age-appropriate instrumental Activities of Daily Living (ADL)
- Grade 3 Severe or medically significant but not immediately life threatening; hospitalization or prolongation of hospitalization indicated; disabling; limiting self-care ADL
- Grade 4 Life-threatening consequences; urgent intervention indicated
- Grade 5 Death related to AE

7.2.3 Adverse Event Relationship to Study Drug

The Investigator must record his/her opinion concerning the relationship of the AE to study therapy (Unrelated, Unlikely, Possibly, Probably, Definitely) on the AE eCRF. See study protocol, Section 12.5 for details.

7.2.4 Serious Adverse Events

An AE or suspected adverse reaction is considered “serious” if in the view of either the investigator

or sponsor, it results in any of the following outcomes:

- Death
- A life-threatening adverse event
- In-patient hospitalization or prolongation of existing hospitalization
- Persistent or significant incapacity or substantial disruption to conduct normal life functions
- A congenital anomaly/birth defect
- Intervention to prevent any one of the other outcomes listed above (based on medical judgment)

7.2.5 Adverse Event Summaries

All AEs (serious and non-serious) occurring after randomization and before the end of study, regardless of relationship to study drug, will be included and classified by SOC and PT using MedDRA.

For TEAEs, the following will be summarized and presented:

- i. An overall summary of TEAEs, which includes:
 - a. the number and percentage of subjects experiencing a TEAE
 - b. the number and percentage of subjects experiencing a TEAE by strongest relationship to study drug
 - c. the number and percentage of subjects experiencing a TEAE by greatest severity
 - d. the number and percentage of subjects experiencing a treatment-emergent SAE
 - e. the number and percentage of subjects experiencing a TEAE leading to death
 - f. the number and percentage of subjects experiencing a TEAE leading to study withdrawal
- ii. the number and percentage of subjects experiencing a TEAE by SOC and PT.
- iii. the number and percentage of subjects experiencing a potentially related TEAE by SOC and PT, where a potentially related TEAE is defined as any TEAE with a causal relationship to study drug assessed as 'Possibly Related', 'Probably Related', or 'Definitely Related'.
- iv. the number and percentage of subjects experiencing a TEAE by SOC, PT and the strongest relationship to study drug
- v. the number and percentage of subjects experiencing a TEAE by SOC, PT and the greatest severity
- vi. the number and percentage of subjects experiencing a treatment-emergent SAE by SOC and PT
- vii. the number and percentage of patients experiencing a TEAE leading to death by SOC and PT

viii. the number and percentage of subjects experiencing a TEAE leading to study withdrawal by SOC and PT

In the overall summary of TEAEs table (i), besides tabulating the number and percentage of subjects, the total number of TEAE episodes will also be provided. If a subject has repeated episodes of a particular TEAE, all episodes will be counted in the summary table.

In the remaining summary tables, the incidence of TEAEs will be calculated by dividing the number of subjects who have experienced the event by the total number of subjects. Thus, the incidence of TEAEs is shown in terms of the total number of subjects and not in terms of the total number of episodes. If a subject has repeated episodes of a particular TEAE, only the most severe episode, or the episode with the strongest causal relationship to study drug, will be counted in the summary tables.

A subject with more than one type of TEAE in a particular SOC or PT will be counted only once in the total of subjects experiencing TEAEs in that particular SOC or PT.

All occurrences of all AEs and SAEs will be listed for each subject, grouped by treatment group. The listing will contain the following information: treatment group, verbatim term, SOC, PT, severity and grade (1-Mild, 2-Moderate, 3-Severe, 4-Life threatening, 5-Death), relationship to study drug, date and day of onset, date and day of resolution or death, action taken with regard to study drug, the outcome, whether the event was an SAE, whether it led to study withdrawal, and whether it is a TEAE. Listings will be sorted by treatment group, subject identification number, onset date, SOC, and PT. If the onset date is completely missing, then these events will be presented first. If the onset date is missing a month or a day, then these events will be presented before any complete dates.

7.3 Pulmonary Function Testing

Spirometry tests including FEV1 (L), % predicted FEV1, FVC (L), % predicted FVC and FEV1/FVC values will be collected at screening and FEV1 (L) will also be recorded at the time points presented in the Appendix A. FEV1 results will be summarized by presenting descriptive statistics of raw data of FEV1 (L) and percent change from each Pre-dose value to Post-dose value on the dosing days.

The proportion of subjects with percent decrease in FEV1 (L) from Pre-dose value to Post-dose value will be presented for each category: >10% and <=12% of reduction; >12% and <=20% of reduction; and >20% of reduction at each measurement time point (Day1, Day 3 and Day 6).

The percent change in FEV1 (L) from Pre-dose value to the protocol defined 30-min Post-dose values will be illustrated in a box/whisker graph on each dosing day by treatment group.

Spirometry results from unscheduled visits will be excluded from table summaries but will be included in the data listing.

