A similar potential pharmacodynamic effect was seen in the spirometry data (specifically the forced expiratory volume in 1 second [FEV1]) from PUL-042-001, likely due to the effect of PUL-042 on the bronchial airways. A dose-dependent decrease in FEV1 was seen with a nadir at approximately 30 minutes post-dose in subjects treated with PUL-042 Inhalation Solution. There was no comparable decline observed with placebo. These measurements were largely within the 12% change from baseline accepted as normal variability. This was followed by a recovery to near baseline levels at 24 hours post dose. Over the course of 7 days, the mean FEV1 was within 0-5% of the baseline value, with the subjects who received higher doses of PUL-042 showing a larger mean decrease in FEV1. None of the decreases in FEV1 were accompanied by signs of respiratory distress or a drop in oxygen saturation. None of the FEV1 results in the PUL-042 inhalation treated groups were statistically different from placebo after the 30-minute time point. The MTD delivered as a single dose was established as 40.6 µg Pam2 : 59.5 µg ODN in PUL-042-001.

A second phase 1 study (PUL-042-003) has been completed. PUL-042-003 was a randomized, open-label, cross-over study to determine the safety and tolerability of PUL-042 Inhalation Solution and to explore the effect of pretreatment with either cromolyn sodium or albuterol sulfate. The primary objective of this study was to determine the safety and tolerability in healthy normal subjects of single or repeated doses of PUL-042 in SWFI. Exploratory objectives include determining whether ANC was an indicator of biological activity and to determine 1) the duration of local biological activity in the bronchial airways by serial FEV1 measurements, 2) whether the administration of cromolyn sodium prior to the administration of PUL-042 had an effect on the FEV1 response, and 3) whether the administration of albuterol prior to the administration of PUL-042 had an effect on the FEV1 response.

In protocol PUL-042-003, the first cohort of 8 subjects (cohort 1) received a dose of 20.3 µg Pam2 : 29.8 µg ODN (1/2 the single-dose MTD of PUL-042) with or without pretreatment with cromolyn sodium (4 each). Subjects were then crossed over to the alternative treatment after a 2-week follow-up period and an additional 2-week washout period.

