A similar design was used for the second cohort (8 subjects) with PUL-042 +/- albuterol sulfate. The second cohort of subjects received a total dose of 40.6 µg Pam2 : 59.5 µg ODN as two doses over 3 days (1 dose on Day 1 and 1 dose on Day 3) and a total dose of 81.2 µg Pam2 : 119 µg ODN as four doses over 32 days (1 dose each on Day 1, Day 3, Day 29 and Day 32).

Results from PUL-042-003 showed no clinically significant abnormalities or changes from baseline for vital signs, electrocardiography, pulse oximetry, physical examination, or safety laboratory assessments.

In general, FEV1 results were consistent with those seen in PUL-042-001 with an early onset decrease in FEV1 in some subjects that spontaneously reversed to near baseline levels over several minutes to hours. In the PUL-042-001 study, a small decrease in average FEV1 was also observed 7 days post-treatment (the last observation in that study) compared to the pre-dose baseline. A similar pattern was observed through 7 days post-treatment in PUL-042-003. Observations at later time points showed sporadic decreases in FEV1 values, but longer-term follow-up measurements of FEV1 gave results comparable to the initial pre-dose baseline values. As in study PUL-042-001, none of the decreases in FEV1 were accompanied by signs of respiratory distress or a drop in oxygen saturation. Pre-treatment with cromolyn sodium or albuterol sulfate had no significant effect on the short lasting FEV1 decreases observed following administration of PUL-042.

Currently there is an ongoing Phase 2 study, PUL-042-402 (A Phase 2, Single-Center, Double-Blind, Placebo-Controlled Study of PUL-042 Inhalation Solution in Rhinovirus-induced Symptoms in Current Smokers with GOLD Stage 0 COPD), that is evaluating the effects of PUL-042 on peak lower respiratory symptoms and safety in subjects with an experimentally induced rhinovirus infection with laboratory human rhinovirus strain HRV A16.

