2.2.3 Safety and Tolerability Endpoints

- Change in forced expiratory volume in 1 second (FEV1) from Pre-dose to Post-dose
- Treatment-emergent serious adverse events (SAEs) through Day 29
- Treatment-emergent adverse events (TEAEs) and severity through Day 29
- Vital signs from Pre-dose to Post-dose

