4.6 Data Derivations and Transformations

The following derivations will be used in this study:

Study Day (Note: There is no day 0 in this study):

- Date of assessment – date of 1st Study Drug administration + 1 for assessments done on or after date of 1st Study Drug administration
- Date of assessment – date of 1st Study Drug administration for assessments done before date of 1st Study Drug administration

Baseline Observation: the last non-missing value prior to 1st Study Drug administration.

Duration:

- Duration in days = end date – start date + 1

- Duration in minutes = end time in minutes – start time in minutes

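### SAP 7.3 plans no within-subject FEV1 change from the first-dose Baseline on Days 3 and 6, so no table counts subjects who cross a threshold from that level

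*SAP*

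**What the plan says.** SAP 2.2.3 gives the FEV1 safety endpoint as "Change in forced expiratory volume in 1 second (FEV1) from Pre-dose to Post-dose". SAP 7.3 carries this out in three ways:

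- **Summary statistics:** descriptive statistics of raw FEV1 in litres, and of "percent change from each Pre-dose value to Post-dose value on the dosing days".
- **Categories:** "The proportion of subjects with percent decrease in FEV1 (L) from Pre-dose value to Post-dose value will be presented for each category". The bands are above 10% to 12%, above 12% to 20%, and above 20%, on Days 1, 3 and 6.
- **Graph:** the change from pre-dose to 30 minutes post-dose "will be illustrated in a box/whisker graph on each dosing day by treatment group".

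SAP 4.6 defines a study-wide reference: "Baseline Observation: the last non-missing value prior to 1st Study Drug administration". SAP 6.2 uses change from baseline for the Ordinal Scale. SAP 7.3 does not use it for FEV1.

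The schedule (Protocol Table 1, SAP Appendix A) has spirometry at screening and then before and 30 minutes after each dose on Days 1, 3 and 6. None is scheduled later.

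On earlier experience, Protocol 5.4 reports for PUL-042-001 that "a small decrease in average FEV1 was also observed 7 days post-treatment" relative to pre-dose, "with the subjects who received higher doses of PUL-042 showing a larger mean decrease in FEV1".

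**The concern.** The regimen is three doses within a week, and its tolerability is a stated objective (Protocol 6.2, SAP 2.1.2). On Day 1 the same-day reference and Baseline normally coincide. On Days 3 and 6 they can differ. If a subject has not fully recovered from an earlier dose, the pre-dose reading is already low, and the planned change measures only the further fall from there.

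A second gap concerns subjects stopped from dosing. Protocol 7.14 and 11.2 keep them on the pre-dose assessment schedule without post-dose assessments, and Protocol 7.11.1 includes spirometry among the pre-dose assessments on Days 3 and 6. Those later readings have no same-day partner, so they cannot enter any change table, and SAP 4.4 imputes nothing. A large FEV1 fall is itself one of the protocol's grounds for stopping dosing (7.10.2, 7.11.2), so these are subjects whose later lung function is of interest.

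At stake is whether the report can say how many subjects in each arm fell by more than 10%, 12% or 20% from their level before the first dose.

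**Working it through.** The plan states no figure to reproduce, so the check is a comparison of reference values followed by an arithmetic illustration.

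**Reference used by each planned FEV1 output**

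| Output in SAP 7.3 | Reference on Days 3 and 6 |
|---|---|
| Raw FEV1 (L) | none (absolute value) |
| Percent change | same-day pre-dose |
| Threshold categories | same-day pre-dose |
| Box plot | same-day pre-dose |

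No output uses the Baseline of SAP 4.6.

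**Inputs to the illustration**

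- Category limits of 10%, 12% and 20%: SAP 7.3.
- *d*, the Day 6 pre-dose deficit relative to Day 1 pre-dose: not given for this trial, so assumed. The nearest documented figure is the Phase 1 mean, within 0-5% of baseline over 7 days (Protocol 5.4).
- *a*, the same-day fall after the Day 6 dose: also assumed.

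**Formula:** fall from Day 1 = 1 − (1 − d)(1 − a). The SAP's category depends on *a* alone.

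| Assumed d | Assumed a | Fall from Day 1 | SAP category (same day) | Category from Day 1 |
|---|---|---|---|---|
| 0% | 10% | 1 − 1.00 × 0.90 = 10.0% | none | none |
| 5% | 10% | 1 − 0.95 × 0.90 = 14.5% | none | above 12% to 20% |
| 8% | 10% | 1 − 0.92 × 0.90 = 17.2% | none | above 12% to 20% |
| 10% | 12% | 1 − 0.90 × 0.88 = 20.8% | above 10% to 12% | above 20% |

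With no deficit the two references agree, so the choice matters only if some decline persists to the next dosing day.

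**Deficit needed to exceed 20% from Day 1:** solve (1 − d)(1 − a) < 0.80.

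- For a = 10%: d > 1 − 0.80/0.90 = 11.1%.
- For a = 12%: d > 1 − 0.80/0.88 = 9.1%.

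Both exceed the 0-5% Phase 1 mean, so a hidden fall above 20% would need an individual well beyond that mean. A move into the middle band needs much less: with a = 10%, d > 1 − 0.88/0.90 = 2.2%.

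**The case against.** The strongest reply is that the plan measures what it set out to measure. The endpoint is the acute post-dose change, Phase 1 put the nadir at about 30 minutes, and no formal safety testing is planned (SAP 7). That is a coherent choice, and the same-day analysis should stay.

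A reader might infer that FEV1 is examined only against same-day values and that cumulative decline is therefore hidden. The documents do not support that. SAP 7.3 also plans descriptive statistics of raw FEV1, SAP 4 gives summaries by treatment group and lists subject data, and subjects stopped from dosing still have pre-dose spirometry scheduled on Days 3 and 6. A drift in pre-dose means could be seen. What these outputs do not give is the within-subject change or the share of subjects beyond a threshold.

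A reader might also infer that Phase 1 showed accumulation. It did not. According to Protocol 5.4, FEV1 recovered to near baseline at 24 hours in PUL-042-001, and the mean stayed within 0-5% of baseline over 7 days. No result on active drug differed statistically from placebo after 30 minutes. PUL-042-001 gave a single dose. PUL-042-003 included repeat dosing and reported a similar 7-day pattern, with longer-term values comparable to the initial baseline. This justifies looking at carry-over and no more.

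Two limits on the remedy also stand. Change from Day 1 mixes any drug effect with the course of COVID-19 and with ordinary variability, and Protocol 5.4 treats changes within 12% as normal, so the lowest band will be partly noise. And because spirometry ends 30 minutes after the Day 6 dose, decline after that reading cannot be seen on any reference.

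**Conclusion.** The concern holds in a limited form. Every planned FEV1 change measure on Days 3 and 6 uses the same day's pre-dose value, and the SAP's own Baseline is not applied to FEV1. The trial would therefore not report individual threshold crossings from before the first dose, and subjects stopped from dosing would leave the change tables from that visit on.

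The size is conditional. With an assumed same-day fall of 10%, a Day 6 deficit of 0-5% corresponds to 10.0-14.5% below Day 1 with no category entered. The 17.2% and 20.8% results rest on assumed deficits of 8% and 10%, which appear in neither document. None of these is an estimate of what will happen in this trial, and nothing here shows that carry-over exists.

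This is a gap in the safety reporting that is cheap to close, not an error in the planned same-day analysis.

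**What to change.** In SAP 7.3, keep the same-day analysis and add, by treatment arm, the percent change from Baseline (SAP 4.6, normally the Day 1 pre-dose value) to each pre-dose and 30-minute FEV1 on Days 3 and 6. Tabulate it in the same three categories. Include the pre-dose readings of subjects who have stopped dosing. State that the results are descriptive, are to be read against placebo, and do not cover the period after the Day 6 post-dose reading.

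Separately, the FEV1 dosing rules in Protocol 7.10.2 and 7.11.2 refer to pre-treatment values without saying whether that means before the first dose or before the same day's dose. The sponsor should reconcile that wording with the reference used in the SAP.

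The cost is one more table and one more figure, with no new visits or measurements. The downside is an output that is open to over-reading if the placebo arm is ignored.
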